### 4.2.3.2 Secondary efficacy variables

The secondary efficacy variables, based on daily seizure diaries, are:

- Percent change from Baseline in 28-day partial-onset seizure frequency
- $\geq 50\%$  reduction in 28-day partial-onset seizure frequency
- $\geq 75\%$  reduction in 28-day partial-onset seizure frequency
- Seizure days per 28 days (subjects with generalized seizures only)
- Seizure-free status

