## 4.3 Selection and withdrawal of subjects

### 4.3.1 Inclusion criteria

All subjects in SP848 must fulfill the following inclusion criteria:

1. A signed informed consent form has been obtained from the parent/legal guardian and assent has been obtained from the subject (when possible or as required according to local Institutional Review Boards [IRBs]/Independent Ethics Committees [IECs]).

4. Subject and caregiver (which may be a parent, legal guardian, or other delegated caregiver) are willing and able to comply with all study requirements, including maintaining a daily seizure diary.

**Subjects who have participated in SP847 or other LCM pediatric clinical studies in epilepsy must fulfill the following inclusion criteria:**

2. Subject has completed SP847 (or the subject discontinued SP847 due to a dose reduction or status epilepticus) for the treatment of uncontrolled partial-onset seizures, or subject has participated in other LCM pediatric clinical studies in epilepsy.
3. Subject is expected to benefit from participation, in the opinion of the investigator.

**Subjects who enroll directly into SP848 without previous participation in a LCM clinical study must fulfill the following inclusion criteria:**

5. Subject is male or female and  $\geq 4$  years to  $\leq 17$  years of age.
6. Subject has a diagnosis of epilepsy with partial-onset seizures.
  - The results of at least 1 prior electroencephalogram (EEG) AND 1 prior magnetic resonance imaging/computerized tomography scan should be consistent with the above diagnosis.
7. Subject has been observed to have uncontrolled partial-onset seizures after an adequate course of treatment (in the opinion of the investigator) with at least 2 AEDs (concurrently or sequentially).
8. Subject has been observed to have at least 2 countable seizures in the 4-week period prior to Screening.
  - In the case of simple partial seizures, only those with motor signs will be counted towards meeting the inclusion criteria (only partial seizures with a recognizable and countable manifestation).
9. Subject is on a stable dosage regimen of 1 to 3 AEDs. The daily dosage regimen of concomitant AED therapy must be kept constant for a period of at least 1 week prior to Screening. Vagal nerve stimulation is not counted as medical therapy; however, VNS settings must be kept constant for a period of at least 1 week prior to Screening.
10. Subject is an acceptable candidate for venipuncture.

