#### **4.3.2 Exclusion criteria**

**Subjects are not permitted to enroll in the study if any of the following criteria are met:**

1. Subject is receiving any investigational drugs or using any experimental devices in addition to LCM.
3. Subject  $\geq 6$  years of age has a lifetime history of suicide attempt (including an actual attempt, interrupted attempt, or aborted attempt), or has suicidal ideation in the past 6 months as indicated by a positive response (“Yes”) to either Question 4 or Question 5 of the Columbia-Suicide Severity Rating Scale (C-SSRS) at Screening.

**Subjects who have participated in SP847 or other LCM pediatric clinical studies in epilepsy are not permitted to enroll in the study if any of the following criteria are met:**

2. Subject meets either of the following:
  - a. Withdrawal criteria for the primary study (with the exception of subjects who discontinued due to a dose reduction or status epilepticus). For subjects entering from EP0060, if the subject (or legal guardian) withdraws consent solely due to route of LCM administration (iv) or if the subject requires more than 10 iv LCM infusions, the subject may be allowed to participant in SP848 after discussion with and agreement from the Medical Monitor.
  - b. Ongoing serious AE (SAE).

**Subjects who enroll directly into SP848 without previous participation in a LCM clinical study are not permitted to enroll in the study if any of the following criteria are met:**

4. Subject has ever received LCM.
5. Subject has any medical or psychiatric condition that, in the opinion of the investigator, could jeopardize or would compromise the subject's ability to participate in this study.
6. Subject has a medical condition that could reasonably be expected to interfere with drug absorption, distribution, metabolism, or excretion.
7. Subject has a known hypersensitivity to any component of the investigational medicinal product.
8. Subject is a female of childbearing potential and does not practice an acceptable method of contraception for the duration of the study.
  - Medically acceptable contraceptive method includes oral or depot contraceptive treatment with at least 30 $\mu$ g ethinylestradiol per intake (or 50 $\mu$ g if associated with carbamazepine [or other strong enzyme inducers, eg, phenobarbital, primidone, oxcarbazepine]) which must be used in conjunction with a barrier method. Sexual abstinence is also an acceptable method of contraception.

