Tests that result in ALT, AST, or ALP up to 25% above the exclusion limit may be repeated once for confirmation. This includes re-screening.

**Subjects who were directly enrolled in EP0060 for iv LCM replacement therapy or to initiate LCM treatment are not permitted to enroll in the study if any of the following criteria are met:**

21. Subjects have previously participated in a long-term, open-label LCM study.

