## 5.1 Screening Visit

Beginning with Protocol Amendment 4, at selected sites, up to approximately 100 eligible pediatric subjects  $\geq 4$  years to  $\leq 17$  years of age who have not previously participated in a LCM clinical study will be permitted to enroll directly into SP848.

At the Screening Visit, subjects entering directly into SP848 (ie, subjects who have not participated in SP847 or another applicable LCM pediatric clinical study in epilepsy) will be evaluated for their suitability for enrollment in SP848. The Screening Visit is not applicable for subjects who have participated in SP847 or another applicable LCM pediatric clinical study in epilepsy; the first visit in SP848 for these subjects is Visit 1 (see Section 5.3).

The Screening assessments will be conducted up to 14 days prior to the first administration of LCM. It is acceptable for the Screening assessments to be conducted on more than 1 day, although it should not be done over longer than 1 week. Prior to the conduct of any study-related procedures, a complete explanation (both verbally and written) of the nature and purpose of the study will be given to the subject (when possible or as required according to local IRBs/IECs) and the subject's parent/legal guardian by the investigator (or designee). The subject's parent/legal guardian will be requested to sign and date the IRB/IEC-approved Informed Consent Form. When possible, or as required by the local IRB/IEC, the subject will be requested to give assent to participate in the study. Each subject's eligibility for the study will be determined on the basis of the inclusion/exclusion criteria and the results of the following pretreatment assessments (for further details of the assessments and the required procedures and methods, please refer to Section 6, Section 7, and Section 8 of this protocol).

- Concomitant medications assessment
- Concomitant AEDs assessment
- Medical history assessment
- Seizure history over the past 4 weeks (historical Baseline)
- Complete physical examination
- Complete neurological examination
- 12-lead ECG (2 interpretable recordings approximately 20 to 30 minutes apart prior to vital signs assessment and collection of blood sample)
- Vital signs assessment (blood pressure and pulse)
- Body weight assessment
- Height assessment
- Blood sample for clinical chemistry, hematology, and endocrinology
- Urine sample for urinalysis
- Serum pregnancy test for female subjects of childbearing potential

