## **6 ASSESSMENT OF EFFICACY**

### **6.1 Seizure counts**

At Screening of SP847 (or other primary study as applicable) or at the Screening Visit of SP848 (for subjects who entered directly into SP848) subjects/caregivers (including parents/legal guardians) will be asked how many seizures the subject has had in the previous 4 weeks; this will serve as a historical Baseline. After the subject is enrolled in the SP848 study, seizure data will be collected in diaries provided to subjects/caregivers (including parents/legal guardians). Each subject/caregiver (including parent/legal guardian) will keep a diary to note daily seizure activity throughout the current study. The subject/caregiver (including parent/legal guardian) should be reminded to bring the diary with them at each clinic visit. The following information will be recorded:

- Seizure type
- Seizure frequency

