### 12.1 Description of statistical methods

Descriptive statistics will be used to provide an overview of the study results. For categorical parameters, these will consist of the number and percentage of subjects in each category. The

denominator for percentages will be based on the number of subjects appropriate for the purpose of analysis. For continuous parameters, descriptive statistics will include the number of subjects (n), mean, standard deviation (SD), median, minimum, and maximum.

Visit 1 of SP847 (or other primary study as applicable) or the Screening Visit of SP848 (for subjects who enter directly into SP848) will serve as Baseline values for safety and efficacy variables unless otherwise noted.

Further statistical methods are presented below, and will be described in more detail in the Statistical Analysis Plan.

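### The 28-day seizure Baseline is assured stable AEDs for only 7 days in direct enrollees and is already on LCM for EP0060 replacement subjects, yet the protocol's efficacy summaries pool them

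*Protocol*

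**What the plan says.** **Seizure Baseline.** Protocol Section 6.1 fixes it as a recalled count. At Screening of the primary study, or of SP848 for direct enrollees, families "will be asked how many seizures the subject has had in the previous 4 weeks; this will serve as a historical Baseline". Section 4.2.3.2 introduces the outcomes differently: "The secondary efficacy variables, based on daily seizure diaries, are" percent change, 50% and 75% responders, and so on. The on-treatment side is a diary; the Baseline side is recall.

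**Direct enrollees.** In Section 4.3.1, criterion 9 states: "The daily dosage regimen of concomitant AED therapy must be kept constant for a period of at least 1 week prior to Screening". It sets the same 1-week minimum for VNS settings. Criterion 8 uses the Baseline weeks for selection: "Subject has been observed to have at least 2 countable seizures in the 4-week period prior to Screening". Exclusion 4 ("Subject has ever received LCM") means that these subjects do have a pre-LCM Baseline.

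**EP0060 subjects.** Exclusion 21 in Section 4.3.2 concerns "Subjects who were directly enrolled in EP0060 for iv LCM replacement therapy or to initiate LCM treatment". EP0060 therefore supplies two kinds of subject: those whose existing LCM is given intravenously for a time, and those starting LCM. Section 1 allows up to 100 EP0060 subjects, within about 400 in total.

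**Analysis.** Sections 12.1.4.1.1 to 12.1.4.1.3 summarize percent change and responders over the overall Treatment Period, with responders counted among all subjects with partial-onset seizures. The optional breakdowns in Sections 4.2.3.3 and 12.1.4.2.4 cover dose, seizure type and classification, time, and completers. None is by LCM exposure at Baseline or by recent AED change.

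**The concern.** The study has no control arm, so Baseline is the only comparator for seizure outcomes. It should represent the seizure rate before LCM on the background treatment that the subject carries into the study. Two features work against this.

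- For direct enrollees, up to 21 of the 28 Baseline days (75%) may fall under another AED dose or VNS setting. The effect of that change is then read as an effect of LCM.
- For EP0060 replacement subjects, the Baseline already contains whatever LCM does. Little further change is to be expected, and these subjects pull the pooled result towards no effect.

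A smaller matter is that the count used as Baseline also admits the subject, so chance highs are retained and chance lows screened out.

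Seizure frequency is a stated objective (Section 3), and Section 12.1.6 foresees reporting in regulatory submissions and publications. As no test is planned, the pooled percent change and responder rate are themselves the result.

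**Working it through.** The protocol states no expected responder rate or effect size, so there is no figure to reproduce. The inputs from it are the 28-day Baseline (Sections 5.1 and 6.1), the 7-day stability minimum and 2-seizure threshold (Section 4.3.1), and the ceilings of 100 and about 400 (Section 1). Everything else is assumed and marked so.

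**1. AED or VNS change inside the Baseline.** Let the change multiply the seizure rate by r (assumed), with d days on the new regimen before Screening, d at least 7. In units of the old rate:

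- Baseline = ((28 − d) + d·r)/28
- on-study rate with no LCM effect = r
- apparent change = r/Baseline − 1

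At d = 7 the Baseline is (21 + 7r)/28:

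| r | Baseline | Apparent change |
|---|---|---|
| 0.9 | 0.975 | −7.7% |
| 0.75 | 0.9375 | −20.0% |
| 0.5 | 0.875 | −42.9% |
| 0.4 | 0.85 | −52.9% |
| 1.25 | 1.0625 | +17.6% |
| 1.5 | 1.125 | +33.3% |

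Such a subject becomes a 50% responder once r is 0.429 or less, and a 75% responder once r is 0.20 or less. The bias shrinks as the change moves back. For r = 0.5, d = 14 gives 0.5/0.75 − 1 = −33.3%, d = 21 gives 0.5/0.625 − 1 = −20.0%, and d = 28 gives zero.

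**2. From subject to table.** A simulation with no LCM effect used gamma-Poisson counts, a 28-day Baseline, entry at 2 or more seizures and 96 weeks of follow-up. Assumed: mean 10 per 28 days, between-subject gamma shape 1, monthly gamma factor of shape 4, changes at d = 7.

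| Share with a change | r | Median change | 50% responders |
|---|---|---|---|
| 0% | – | −1.0% | 11.4% |
| 25% | 0.75 | −6.2% | 14.1% |
| 25% | 0.5 | −12.5% | 19.2% |
| 50% | 0.5 | −24.5% | 27.0% |

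**3. Selection on the Baseline count.** Take a constant true rate λ per 28 days, a Poisson Baseline count N, and follow-up long enough to show λ (all assumed). A subject is a false 50% responder when N is at least 2λ, so the rate is P(N ≥ 2λ)/P(N ≥ 2).

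- λ = 2: 0.143/0.594 = 24%.
- λ = 4: 0.051/0.908 = 5.6%. Without the threshold it would be 5.1%, so here nearly all of it is ordinary chance.

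**4. On-LCM Baseline.** With a share w already on LCM at Baseline, responder rate q in them and p in the others, the pooled rate is (1 − w)p + wq. Take p = 50% and q = 0 to 20% (assumed).

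- w = 100/400 (every EP0060 subject, the extreme): 37.5% to 42.5%.
- w = 50/400: 43.8% to 46.3%.

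**The case against.** **Stakes.** There is no primary efficacy variable, the efficacy data are called preliminary, and no test is planned. AEDs may also be raised, added or withdrawn during treatment, so on-study change is never due to LCM alone. All of this stands. It limits the harm to interpretation; it does not repair the comparator.

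**Size of the AED effect.** Criterion 9 sets a minimum and also asks for a stable regimen in general terms. Criterion 7 requires seizures uncontrolled after at least 2 AEDs, so a step that halves seizures may be uncommon. A reader might take 43% as the bias of the study result. The documents do not support that: it is a conditional figure for one subject, and neither the share affected nor the effect size is given. Nor is the direction fixed, since a recent AED reduction makes a subject look worse.

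**Regression to the mean.** A reader might infer that the entry threshold produces a general spurious reduction. For the per-subject percent change that the protocol uses, the same Poisson model gives mean −23% and median −33% at 2 per 28 days, but mean +10% and median 0% at 4. Only the excess of chance responders near the threshold holds.

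**EP0060.** Section 12.1 gives "Visit 1 of SP847 (or other primary study as applicable) or the Screening Visit of SP848" as the general Baseline, which might suggest that rollovers' seizure Baseline is Visit 1. That rule applies unless otherwise noted, and Section 6.1 specifies the 4-week count at primary-study Screening. It is also tempting to say that these subjects face no minimum seizure count, leaving percent change undefined. SP848 sets none for rollovers, but EP0060's own criteria are not shown. Finally, an on-LCM Baseline hides nothing if LCM has no effect.

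**Left to the SAP.** Section 12.1.4.2.4 defers detail to the SAP, which could separate these groups. The Baseline definition, stability window and pooled summaries, however, are fixed in the protocol.

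**Conclusion.** The point holds in a limited form and is worth correcting. Criterion 9 secures constant AEDs and VNS settings for 7 of the 28 Baseline days in direct enrollees. A change in the other 21 days can move an affected subject's result either way, by 43% in the halving example at d = 7. The effect on the pooled table depends on a share that the documents do not give; under the assumptions above, 25% of subjects with such a step would raise the no-effect 50% responder rate from 11.4% to 19.2%.

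Selection on the Baseline count adds chance responders mainly at rates near the entry threshold. EP0060 replacement subjects dilute any real LCM effect. That they were on LCM at primary-study Screening is inferred from their entry for replacement; their number is unknown, and 100 is the ceiling for all EP0060 subjects. No error rate is affected.

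**What to change.** Amend Section 12.1.4.1 as follows.

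- **(a)** Base percent change and the 50% and 75% responder summaries on subjects whose Baseline precedes LCM. Show subjects already on LCM at Baseline in a separate table.
- **(b)** Repeat these summaries without direct enrollees who had any AED or VNS change in the 28 days before Screening. First confirm that the dates are recorded: Section 5.1 lists a concomitant AED assessment but does not say how far back it reaches, and its list does not name VNS settings.

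With (b), the mixture term in step 1 disappears; chance variation and the entry threshold remain. With (a), the dilution in step 4 disappears.

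The cost is analysis wording and smaller numbers in the restricted tables. Eligibility, dosing and visits do not change. Using the diary kept between Screening and the first Titration Visit as an alternative Baseline is not advised. It covers at most about 14 days, and at 2 seizures per 28 days e^−1 = 37% of subjects would record none (Poisson), leaving percent change undefined.

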#### **4.3.2 Exclusion criteria**

**Subjects are not permitted to enroll in the study if any of the following criteria are met:**

1. Subject is receiving any investigational drugs or using any experimental devices in addition to LCM.
3. Subject  $\geq 6$  years of age has a lifetime history of suicide attempt (including an actual attempt, interrupted attempt, or aborted attempt), or has suicidal ideation in the past 6 months as indicated by a positive response (“Yes”) to either Question 4 or Question 5 of the Columbia-Suicide Severity Rating Scale (C-SSRS) at Screening.

**Subjects who have participated in SP847 or other LCM pediatric clinical studies in epilepsy are not permitted to enroll in the study if any of the following criteria are met:**

2. Subject meets either of the following:
  - a. Withdrawal criteria for the primary study (with the exception of subjects who discontinued due to a dose reduction or status epilepticus). For subjects entering from EP0060, if the subject (or legal guardian) withdraws consent solely due to route of LCM administration (iv) or if the subject requires more than 10 iv LCM infusions, the subject may be allowed to participant in SP848 after discussion with and agreement from the Medical Monitor.
  - b. Ongoing serious AE (SAE).

**Subjects who enroll directly into SP848 without previous participation in a LCM clinical study are not permitted to enroll in the study if any of the following criteria are met:**

4. Subject has ever received LCM.
5. Subject has any medical or psychiatric condition that, in the opinion of the investigator, could jeopardize or would compromise the subject's ability to participate in this study.
6. Subject has a medical condition that could reasonably be expected to interfere with drug absorption, distribution, metabolism, or excretion.
7. Subject has a known hypersensitivity to any component of the investigational medicinal product.
8. Subject is a female of childbearing potential and does not practice an acceptable method of contraception for the duration of the study.
  - Medically acceptable contraceptive method includes oral or depot contraceptive treatment with at least 30 $\mu$ g ethinylestradiol per intake (or 50 $\mu$ g if associated with carbamazepine [or other strong enzyme inducers, eg, phenobarbital, primidone, oxcarbazepine]) which must be used in conjunction with a barrier method. Sexual abstinence is also an acceptable method of contraception.
  - The subject must understand the consequences and potential risks of inadequately protected sexual activity, be educated about and understand the proper use of contraceptive methods, and undertake to inform the investigator of any potential change in status. Females of childbearing potential must have a negative pregnancy test at the Screening Visit.
9. Subject has a creatinine clearance less than 30mL/min.
10. Subject has a clinically relevant ECG abnormality, in the opinion of the principal investigator (ie, second or third degree heart block at rest or a QT prolongation greater than 450ms).
11. Subject has hemodynamically significant heart disease (eg, heart failure).
12. Subject has an arrhythmic heart condition requiring medical therapy.
13. Subject has a known history of severe anaphylactic reaction or serious blood dyscrasias.

14. Subject has nonepileptic events, including psychogenic seizures, that could be confused with seizures. If both epileptic and nonepileptic events are present, epileptic events must be distinguished from nonepileptic phenomena.
15. Subject has a history of primary generalized epilepsy.
17. Subject is taking monoamine oxidase inhibitors-A (MAOI-A) or narcotic analgesics.
18. Subject has epilepsy secondary to a progressing cerebral disease or any other progressively neurodegenerative disease, such as Rasmussen syndrome.
19. Subject has a known sodium channelopathy, such as Brugada syndrome.
20. Subject has  $>2$ x upper limit of normal (ULN) of any of the following: alanine aminotransferase (ALT), aspartate aminotransferase (AST), alkaline phosphatase (ALP), or  $>$ ULN total bilirubin ( $\geq 1.5$ xULN total bilirubin if known Gilbert's syndrome). If subject has elevations only in total bilirubin that are  $>$ ULN and  $<1.5$ xULN, fractionate bilirubin to identify possible undiagnosed Gilbert's syndrome (ie, direct bilirubin  $<35\%$ ).

For randomized subjects with a Baseline result  $>$ ULN for ALT, AST, ALP, or total bilirubin, a Baseline diagnosis and/or the cause of any clinically meaningful elevation must be understood and recorded in the electronic Case Report form (eCRF).

If subject has  $>$ ULN ALT, AST, or ALP that does not meet the exclusion limit at screening, repeat the tests, if possible, prior to dosing to ensure there is no further ongoing clinically relevant increase. In case of a clinically relevant increase, inclusion of the subject must be discussed with the Medical Monitor.

Tests that result in ALT, AST, or ALP up to 25% above the exclusion limit may be repeated once for confirmation. This includes re-screening.

**Subjects who were directly enrolled in EP0060 for iv LCM replacement therapy or to initiate LCM treatment are not permitted to enroll in the study if any of the following criteria are met:**

21. Subjects have previously participated in a long-term, open-label LCM study.

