#### **4.3.3 Criteria for withdrawal**

All subjects discontinuing treatment with study medication for any reason should taper off medication as described in Section 4.4.1. Whenever possible, these cases should be discussed with the medical monitor prior to withdrawing the subject from the study. All subjects who withdraw from the study due to an AE must be followed until resolution of the event or until the event is considered stable. The following criteria for subject withdrawal from SP848 are outlined below. Additional discontinuation criteria for potential drug-induced liver injury (PDILI) are presented in Section 4.3.3.1.

Participation in this study **must** be discontinued for any of the following reasons:

1. Intolerable AEs, including clinically relevant abnormal laboratory findings that, in the opinion of the investigator, preclude further participation in the study
2. The request of the Sponsor or a Regulatory Agency

3. Subject achieves menarche during the study and does not practice an acceptable method of contraception for the duration of the study (unless sexually abstinent).
4. Subject becomes pregnant, as evidenced by a positive pregnancy test.
5. Subject has a corrected QT interval (QTc) of greater than or equal to 500ms as confirmed by a cardiologist overread on any ECG.
6. Subject develops a second-degree atrioventricular (AV) block while awake or develops a third-degree AV block at any time.
7. Subject is unwilling or unable to continue, or the caregiver/parent/legal guardian is unwilling or unable to allow the subject to continue in the study.
8. Investigator's decision that withdrawal from further participation would be in the subject's best interest.
9. Subject experiences convulsive status epilepticus (if none had occurred prior to study entry) and is compliant with study treatment
11. For subject who did not complete a C-SSRS at Screening, subject has a lifetime history (prior to study entry or since study start) of suicide attempt (including an actual attempt, interrupted attempt, or aborted attempt) of the screening version of the C-SSRS. The investigator must withdraw the subject from the study and immediately refer the subject to a Mental Healthcare Professional.

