- f Subjects who complete the study or withdraw prematurely from the study, and who discontinue use of LCM (ie, taper), should complete the Final Visit 2 weeks after the final dose of study medication. The Final Visit is not required for subjects who participate in EP0151 or EP0152.
- g This TC occurs 28 to 35 days after the last dose of LCM. The Safety Follow-Up TC is not required for subjects who participate in EP0151 or EP0152.

- h For subjects enrolling from SP847 or other LCM pediatric clinical studies in epilepsy, assessments may have been done as part of the last visit of the primary study. For subjects enrolling directly into SP848, these assessments should be completed at Visit 1.
- i All subjects will be required to have a 12-lead ECG (2 interpretable recordings) conducted at LCM  $C_{max}$  1 week after an initial LCM dose increase to a LCM dose level that is  $\geq 8\text{mg/kg/day}$  or a new concomitant AED is introduced. This ECG can be conducted at an Unscheduled Visit, if necessary. Subjects having a LCM dose increase to  $\geq 8\text{mg/kg/day}$  will be required to arrive at the clinic prior to taking their morning dose of LCM. Subjects will be administered their morning LCM dose by study personnel at the clinic so that an ECG (2 interpretable recordings approximately 20 to 30 minutes apart prior to vital signs assessment) can be performed 30 minutes to 1 hour after the administration of LCM (ie, at LCM steady state  $C_{max}$ ).
- j For subjects enrolling from EP0060, these assessments should be completed at Visit 1.
- k Blood samples may be drawn at any time post-dosing with LCM.
- l For female subjects of childbearing potential, serum pregnancy tests will be performed at Visit 1, the Early Termination Visit, and the Final Visit. Urine pregnancy tests will be performed at Visits 2, 3, 4, 5, 6, 7, 8, and 9.
- m The Tanner Stage will be performed only for subjects who are pubescent at Visit 1 or who will enter puberty during the course of the study.

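### SP848 sets no contraception requirement for rollover girls who are already past menarche at entry

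*Protocol*

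**What the plan says.** Section 4.3.2 of the Protocol sorts the exclusion criteria by route of entry. Criteria 1 and 3 bind everyone and concern other investigational products and suicidality. Criterion 2 binds rollovers. It bars a subject who meets the "Withdrawal criteria for the primary study (with the exception of subjects who discontinued due to a dose reduction or status epilepticus") or who has an ongoing SAE. Criterion 21 binds subjects who entered EP0060 directly and concerns earlier long-term open-label participation.

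The contraception rule is criterion 8: "Subject is a female of childbearing potential and does not practice an acceptable method of contraception for the duration of the study". It falls under the heading that begins "Subjects who enroll directly into SP848 without previous participation in a LCM clinical study are not permitted to enroll in the study if". Its sub-items define acceptable methods, ask the girl to report a change in status, and add that "Females of childbearing potential must have a negative pregnancy test at the Screening Visit".

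In Section 4.3.3, two must-withdraw criteria are relevant. Criterion 3 reads "Subject achieves menarche during the study and does not practice an acceptable method of contraception for the duration of the study (unless sexually abstinent"). Criterion 4 reads "Subject becomes pregnant, as evidenced by a positive pregnancy test".

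On visits, Section 5.1 states that "The Screening Visit is not applicable for subjects who have participated in SP847 or another applicable LCM pediatric clinical study in epilepsy". Rollovers start at Visit 1. On testing, Table 16-1 states "For female subjects of childbearing potential, serum pregnancy tests will be performed at Visit 1, the Early Termination Visit, and the Final Visit"; urine tests follow at Visits 2 to 9, and Table 16-2 adds Visits 10 to 13.

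**The concern.** Each criterion is sensible on its own terms, and criterion 8 and must-withdraw 3 do not contradict each other. Together they leave one group out: girls who arrive from a primary study already past menarche. A rollover who reaches menarche the week after Visit 1 must use contraception, be abstinent or be withdrawn. One who reached it the week before Visit 1 is under no SP848 rule. No rationale is given for the difference.

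The group is not hypothetical. Section 1 allows rollovers up to 18 years of age, and the schedule provides pregnancy tests for rollovers of childbearing potential. The protocol does not state the purpose of the contraception rule. Its evident purpose is to keep a fetus from being exposed to study treatment, and for these girls SP848 provides detection without prevention.

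The matter is one of subject safety. No analysis set, endpoint or estimate is affected.

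**Working it through.** **Scope check.** The question is which subjects each rule binds. Four situations arise:

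| Situation | Contraception rule at entry | Contraception rule during SP848 |
|---|---|---|
| Direct enrollee, past menarche at entry | Exclusion 8 | Exclusion 8 asks for contraception throughout, but no must-withdraw criterion enforces it |
| Direct enrollee reaching menarche on study | Not yet relevant | Must-withdraw 3 |
| Rollover reaching menarche on study | Not yet relevant | Must-withdraw 3 |
| Rollover, past menarche at entry | None in SP848; whatever exclusion 2a carries over from the primary study | None |

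The last row is the gap. The inclusion criteria for all subjects and for rollovers (Section 4.3.1) do not mention contraception either. Section 8.1.6 deals only with what happens once a pregnancy is known.

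**What remains for that last group after entry.**

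- Must-withdraw 2 (request of the sponsor or a regulator) and must-withdraw 8 (investigator's decision) depend on someone's judgement.
- May-withdraw 3 (noncompliance) is optional, and no contraception requirement is stated for this girl to breach.
- Must-withdraw 4 is mandatory but acts only once a pregnancy test is positive.

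**How long the gap lasts and how often the backstop operates.** Inputs: visit weeks and pregnancy-test rows in Tables 16-1 and 16-2; the ±7-day window in Section 5.

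- Tests at Weeks 0, 4, 8, 12, 20, 28, 36, 44, 52, 60, 72, 84 and 96: 13 tests (serum at Visit 1, urine at Visits 2 to 13).
- Intervals: 3 × 4 + 6 × 8 + 3 × 12 = 12 + 48 + 36 = 96 weeks.
- Largest planned interval: 12 weeks, in Year 2.
- Largest interval with one visit 7 days early and the next 7 days late: 12 weeks + 14 days = 14 weeks.

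These figures describe the backstop, not the number of girls exposed. The same schedule from Visit 1 applies to direct enrollees, who do have a contraception rule at entry.

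**Number affected.** Section 12.2 gives about 42 eligible subjects from SP847, and Section 1 gives about 200 from other lacosamide studies. These counts cover both sexes and all ages. The protocol gives no share by sex, menarche or contraceptive use, so no count can be derived.

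**The case against.** The strongest reply is that the split is deliberate. Every rollover comes from a primary study, and exclusion 2a makes that study's withdrawal criteria a mandatory bar. The appended amendment history shows that the menarche rule dates from when SP848 took only rollovers. It would be natural for the primary study to vet girls already past menarche and for SP848 to add those who reach it later. Criterion 8 would then be needed only for direct enrollees, who have no primary study. This may well explain how the text arose, and the primary protocols may reduce the gap at entry. But 2a is tested once, at entry. It sets no condition for the following 96 weeks, whereas contraception is a continuing condition, as criterion 8 itself says.

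A second reply is that Section 5.3 already bases a rollover's eligibility on the Visit 1 assessments, including the serum pregnancy test. That stands: tying the negative test to Visit 1 makes existing practice explicit. A negative test still does not require contraception.

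A third is that criterion 8 obliges the girl to report a change in status. That undertaking binds direct enrollees only, and it is not a withdrawal rule.

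Finally, these girls already take lacosamide and are expected to benefit, so a wider mandatory withdrawal rule works against the continued-access objectives in Section 3. This is a real cost. It is limited because abstinence counts as compliance, and the protocol already accepts the same cost for girls who reach menarche on study.

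**Conclusion.** The concern holds. Followed as written, SP848 places no contraception condition on a rollover girl who is past menarche at entry, for up to 96 weeks of treatment. Her only safeguard during treatment that does not rest on discretion is pregnancy testing at intervals of up to 12 weeks (14 with windows), followed by withdrawal if positive. A lesser gap of the same kind exists for a direct enrollee who stops contraception after entry: criterion 8 expects contraception throughout, but no must-withdraw criterion enforces it.

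The conclusion on the on-study period rests on the current protocol text alone. How many girls are uncovered at entry depends on the primary protocols, which are not shown, and the number affected is unknown. It is a safety gap that should be closed. It does not threaten the study's analyses.

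**What to change.** Three wording changes by amendment:

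1. Move exclusion 8 to the exclusions that apply to all subjects, leaving the accepted methods as the sponsor has defined them.
2. Tie its negative pregnancy test to the first SP848 visit: Screening for direct enrollees, Visit 1 for rollovers.
3. Reword must-withdraw criterion 3 to cover any subject who is, or during the study becomes, a female of childbearing potential and does not use an acceptable method, with abstinence accepted. This also closes the gap for direct enrollees who stop after entry.

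No new test is required, because the Visit 1 serum test already applies to rollovers. The cost is the amendment itself and the possibility that some rollover girls, in a number that cannot be estimated from the protocol, would have to meet the condition to enter or to stay on lacosamide in SP848.
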